#### **4.1 Sample Size Estimation**

The primary objective of this study is to evaluate the safety of ALM-488 administered by intravenous (IV) infusion to subjects undergoing head and neck surgery.

At each dose level, a cohort of 3 subjects will be enrolled for safety and tolerability evaluation. If there are no subjects with a DLT at a given dose level, new subjects will be enrolled at the next dose escalation level. If there are  $\geq 1$  subjects having any DLT, the enrollment to that specific dose and dose escalation will stop. New subjects will be enrolled at the next dose de-escalation level. There will be a minimum of 3 cohorts. Given that there will be 3-6 subjects for each dose level, 9-36 subjects will be needed for the dose escalation/de-escalation cohorts.

It is anticipated that the proposed dose range (100-1000mg) is expected to yield optimal imaging performance, with an initial starting dose of 100mg that has been selected based on supportive nonclinical testing. If the 100 mg dose is found to provide adequate fluorescence imaging of nerves, a dose de-escalation schedule will be followed to ensure that the lowest effective dose is determined. If imaging at starting first de-escalated dose (75 mg) becomes less adequate compared to 100mg as determined by the SRC, then imaging at dose escalation schedule will resume - beginning at 200mg. The Optimal Dose will be determined by the SRC as the lowest possible dose and toxicity profile that achieves adequate imaging performance of nerves using WLR combined with FL.

The Dose Timing Cohort will use the Optimal Dose as defined by the SRC following completion of the Dose Escalation/De-Escalation cohorts. Subjects in the Dose Timing phase will be administered ALM-488 at two planned operative times before surgery to assess the impact of timing of administration on fluorescence image quality. This phase will consist of 2 cohorts, 6 subjects/cohort: (1) dose administration 3-5 hours in advance of surgery, (2) dose administration 1-3 hours in advance of surgery. A total of 12 subjects will be needed for the Dose Timing phase.

In summary, 9-36 subjects may be enrolled into the dose escalation/dose de-escalation cohorts and 12 subjects may be enrolled into the dose timing cohort. A total of 21-48 subjects may be enrolled into this study.

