### **5 Analysis Sets and Cohorts**

Analysis Sets are described as follows:

- Enrolled analysis set (ENR) defined as all subjects who provided informed consent.
- Safety Analysis Set (SAF), defined as all subjects who received at least one dose of ALM-488

QMS Document Name: Statistical Analysis Plan	Page 9 of 29
QMS No (include version ref): STF-015-GL.02	Document date: 09JUL2019
CONFIDENTIAL	

- Dose-Limiting Toxicity (DLT) Evaluable Set, defined as subjects who receive ALM-488 and either 1) complete the safety follow-up through the DLT evaluation period (i.e., Day 15 ± 8) or 2) experiences a DLT at any time during the DLT evaluation period.
- Activity Analysis or Full Analysis Set (FAS), defined as all subjects in SAF who also received at least one evaluable image.
- Pharmacokinetics (PK) Analysis Set defined as all subjects who completed a PK blood sampling period without any major protocol violations which would render the data unreliable. The PK will be the primary analysis set for the pharmacokinetic analyses. PK of analyses will be fully described in the PK SAP.

SAF will be used for all safety analyses. FAS will be used for all efficacy analyses. The PK Analysis Set will be used for all PK analyses; ENR set will be the primary analysis set for disposition and listings. PP set will constitute the primary analysis set for early efficacy. DLT Evaluable Analysis Set will be used to assess the tolerability of ALM-488 in the dose escalation phase.

The Dose Escalation/De-Escalation cohort (Cohort A) consists of all dose escalation/de-escalation cohorts: Cohort A1, A2, A3, A4, A5, A6. In case of DLT rate = 0 or special FDA requests additional cohorts may be added to the tables.

The Dose Time Determination cohort (Cohort B) consists of: Cohort B1 - dose administration 3-5 hours in advance of surgery, and Cohort B2 - dose administration 1-3 hours in advance of surgery.

If not otherwise stated in the respective section, the statistical analyses will be performed for the following analysis sets:

Analyses	ENR	FAS	DLT	SAF	PK
Disposition	✓				
Demographics and baseline characteristics				✓	
Medical history				✓	
Exposure and compliance				✓	
Previous and concomitant therapies				✓	
Early Efficacy		✓			
Pharmacokinetic					✓
Safety				✓	
Dose-Limiting Toxicity			✓		
Listings		✓		✓	

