### **7.2 Secondary Endpoints**

The endpoints to characterize the PK of ALM-488 will be fully described in the PK SAP.

The endpoints to determine the dose of ALM-488 needed to generate an adequate fluorescence signal in nerves include the following:

- Timing of administration of ALM-488 relative to surgery

QMS Document Name: Statistical Analysis Plan	Page 11 of 29
QMS No (include version ref): STF-015-GL.02	Document date: 09JUL2019
CONFIDENTIAL	

- Dose
- Intensity (signal-to-background ratio- SBR)
- Surgeon rating scale

The endpoints to determine the dose of ALM-488 needed to generate an adequate fluorescence signal in nerves will be summarized for each of Cohorts A1-A6, as well as overall for Cohort A.

The endpoints to evaluate the effect of timing of administration of ALM-488 relative to surgery on adequacy of fluorescence nerve labeling include the following:

- Timing of administration of ALM-488 relative to surgery
- Time from injection to skin incision
- Intensity (SBR)
- Surgeon rating scale

The endpoints to evaluate the effect of timing of administration of ALM-488 relative to surgery on adequacy of fluorescence nerve labeling will be summarized for each of Cohorts B1 and B2, as well as overall for Cohort B.

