#### **13 Efficacy**

The data on the signal-to-background ratio for FL and WLR will be provided by Stanford University for the different regions of interest ROIs. All efficacy analyses will be completed on the FAS Analysis Set and will be repeated in PP analysis set if the latest is different from FAS Analysis Set. The analyses using signal to background ratio SBR for cohort A will only use images produced by Zeiss camera while both Zeiss and OnLume devices will be used for timing cohort B.

QMS Document Name: Statistical Analysis Plan	Page 18 of 29
QMS No (include version ref): STF-015-GL.02	Document date: 09JUL2019
CONFIDENTIAL	

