### **13.1 Timing, Dose, Size and Intensity**

The efficacy endpoints pertaining to timing of administration, dose, and intensity (signal-to-background ratio SBR), along with the surgeon rating scale will be assessed throughout enrollment into Cohorts A1-A6 to determine the final dose for use in Cohorts B1 and B2. These efficacy endpoints will also be used to evaluate the effect of timing of administration of ALM-488 by comparison of Cohort B1 and B2. The following analyses are planned for these efficacy endpoints:

- For each Cohort, SBR will be averaged to get a single mean ratio per patient; then a paired t-test or Wilcoxon signed rank test will be used, as appropriate, to compare SBR between FL and WLR.
- SBR will be also listed by cohort type, and surgery type and device for both FL with WLR.
- Image intensity ratios will also be analyzed with repeated measures analysis of variance (RMANOVA) with timing, image, method (FL /WLR), and device (Zeiss/OnLume) as the repeated factors in the model.
- SBR for FL and WLR measurements will be plotted. Values to the right of the line will indicate that there is improved visualization with FL images and values to the left of the line will indicate that there is improved visualization with WLR images(Equal performance of FL versus WLR will be indicated by dashed line (slope = 1)].
- To further assess timing, Cohorts B1 and B2 will be compared. Image ratios will be averaged to get a single mean ratio per patient; then an unpaired t-test or Wilcoxon rank sum test will be used, as appropriate, separately for FL and WLR.

Paired t-tests will be used unless markedly non-normal data is observed including bimodal or other severe assumption violations; minor skewness is robust to the paired t-test and RMANOVA assumptions. If extreme skewness with outliers, or bimodal distributions are observed, then a Wilcoxon signed rank test will be used instead of a paired t-test and RMANOVA will be performed on the ranked data.

Similarly, unpaired t-tests will be used unless markedly non-normal data is observed including bimodal or other severe assumption violations; minor skewness is robust to the unpaired t-test assumptions. If extreme skewness with outliers, or bimodal distributions are observed, then a Wilcoxon rank sum test will be used instead.

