#### EFFICACY

- Table 14.2.2.1 SBR comparison between FL and WLR, Zeiss camera Cohort A Analysis Set: FAS
- Table 14.2.2.2 SBR comparison between FL and WLR, Cohort B Analysis Set: FAS

- Table 14.2.3.1 SBR comparison between FL and WLR – Zeiss Image Analysis, Cohort A Analysis Set: FAS
- Table 14.2.3.2 SBR comparison between FL and WLR – Image Analysis, Cohort B Analysis Set: FAS

- Table 14.2.4.1 SBR comparison between B1and B2 – FL Analysis Set: FAS

- Table 14.2.4.2 SBR comparison between B1 and. B2– WLR Analysis Set: FAS

- Table 14.2.5.1 Surgeon Rating Scale, Cohort A Analysis Set: FAS

- Table 14.2.5.1 Surgeon Rating Scale, Cohort B Analysis Set: FAS

- Table 14.2.6.1 Correlation Between Surgeon Rating Scale and SBR for Zeiss device, Cohort A - Analysis Set: FAS

- Table 14.2.6.2 Correlation Between Surgeon Rating Scale and SBR, Cohort B Analysis Set: FAS

- Table 14.2.7.1 SBR and Surgeon Rating Scale for Zeiss device Cohort A, FL Analysis Set: FAS

- Table 14.2.7.2 SBR and Surgeon Rating Scale Cohort B, FL Analysis Set: FAS

- Table 14.2.8 Optimal cut-off point of SBR Cohort A and B, FL- Analysis Set: FAS

- Table 14.2.9.1 Surgeon nerve dissecting time saved, Cohort A Analysis Set: FAS

- Table 14.2.9.1 Surgeon nerve dissecting time saved, Cohort B Analysis Set: FAS

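### SAP 13.1 makes timing a repeated factor in the RMANOVA of signal-to-background ratio, but each patient has only one administration time, so there is no within-patient timing contrast

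*SAP*

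**What the plan says.** SAP section 13.1 lists several analyses of the signal-to-background ratio (SBR) under fluorescence (FL) and white light reflectance (WLR). Two of them bear on timing.

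- A repeated measures ANOVA (RMANOVA) of the image ratios, "with timing, image, method (FL /WLR), and device (Zeiss/OnLume) as the repeated factors in the model". No between-patient factor and no error term is named.
- A comparison of Cohorts B1 and B2 on one mean ratio per patient; "then an unpaired t-test or Wilcoxon rank sum test will be used, as appropriate, separately for FL and WLR".

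The design behind these is in other sections. Section 5 defines "Cohort B1 - dose administration 3-5 hours in advance of surgery, and Cohort B2 - dose administration 1-3 hours in advance of surgery". Section 4.1 gives the size: "This phase will consist of 2 cohorts, 6 subjects/cohort", and "A total of 12 subjects will be needed for the Dose Timing phase". Section 7.2 lists two timing measures: when ALM-488 is given relative to surgery, and "Time from injection to skin incision". In section 20.1 the tables titled for timing are 14.2.4.1 (FL) and 14.2.4.2 (WLR), the first headed "SBR comparison between B1and B2".

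**The concern.** A repeated factor has to take more than one level within the same patient. Method does, since FL and WLR are compared within patients. Timing of administration does not: a patient belongs to B1 or to B2, and both timing measures in section 7.2 have a single value per patient. Section 13.1 therefore treats timing as within-patient in one bullet and as between-patient in another.

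The effect of timing on nerve labelling is a secondary objective (SAP 6.2). A program that follows the RMANOVA sentence literally could produce a timing p-value that is too small and disagrees with the B1 v B2 test on the same 12 patients. The SAP does not say which of the two results governs.

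**Working it through.** **Plan's own figure.** 2 cohorts × 6 patients = 12, as section 4.1 states. No effect size, standard deviation or power is given for this phase, so there is no power figure to reproduce.

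**Estimability (12 patients, no assumption about correlation).** Take 10 images per patient, with one indicator column per patient. The design matrix has rank 12. Adding a timing column (B1 = 0, B2 = 1) leaves the rank at 12, because that column is the sum of the six B2 patient columns. A second layout with patient, image (4), method and device terms gives rank 17 without timing and 17 with it. The within-patient sum of squares of timing is 0. The number of images does not matter, and neither does the section's fallback of analysing ranks, because ranking changes the response and not the design. Timing-by-method does add 1 to the rank, so that interaction is estimable.

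**Size of the error if timing is tested against within-patient error.** The SAP gives no image count, correlation or error term. Assumed: 6 v 6 patients, m images per patient, one ratio per image, intraclass correlation ICC, total variance 1, no true timing effect.

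- True variance of a patient mean: ICC + (1 − ICC)/m.
- Variance the test would use: (1 − ICC)/m, on 12(m − 1) degrees of freedom.
- Ratio: k = [ICC + (1 − ICC)/m] / [(1 − ICC)/m].
- Type I error = P(|t_df| > t(0.975, df)/√k).

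| m, ICC | k | df | t(0.975)/√k | Type I error |
|---|---|---|---|---|
| 3, 0.2 | 0.4667/0.2667 = 1.75 | 24 | 2.064/1.323 = 1.560 | 0.132 |
| 5, 0.5 | 0.6/0.1 = 6.0 | 48 | 2.011/2.449 = 0.821 | 0.416 |
| 10, 0.7 | 0.73/0.03 = 24.33 | 108 | 1.982/4.933 = 0.402 | 0.689 |

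A simulation of the same settings (40,000 runs) agrees, and shows how often the two planned analyses would conflict:

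| m, ICC | Within-patient error | Patient-level t-test | RMANOVA p < 0.05, t-test not | Reverse |
|---|---|---|---|---|
| 3, 0.2 | 0.134 | 0.051 | 0.091 | 0.007 |
| 5, 0.5 | 0.414 | 0.049 | 0.367 | 0.000 |
| 10, 0.7 | 0.688 | 0.047 | 0.638 | 0.000 |

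With unequal image counts (2-10 per patient), the patient-level t-test still gives 0.049, 0.051 and 0.051 at ICC 0.2, 0.5 and 0.7. A separate simulation with milder assumptions (2-8 ratios, ICC 0.1-0.5) puts the within-patient-error test at 0.07-0.51.

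**The case against.** The strongest objection is that a sensible programmer would not do this. *Repeated factors* is often used loosely, and a common implementation puts timing in the mean model and lets images correlate within patient. With balanced data and compound symmetry, the timing statistic from that model equals the patient-mean t-statistic. With 10 degrees of freedom it is the same test. Even with the wrong 12(m − 1), the type I error would be only P(|t_10| > 2.064, 2.011, 1.982) = 6.6%, 7.2% and 7.6%. This stands: such a program is close to valid, and the 13%-69% range belongs to one error-term choice and to assumed inputs. If the software instead drops timing as inestimable, no misleading p-value appears. But a program that enters timing between patients departs from the sentence as written.

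The output plan also limits the harm. Tables 14.2.3.1 and 14.2.3.2 appear to be the image-level outputs. They are titled for FL v WLR and are already split by cohort, and no listed table is titled for an RMANOVA timing result. This stands too, and it supports a low severity.

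Two alternative readings are weak. Section 4.1 refers to dosing at two planned times, but its next sentence resolves this into two cohorts. Timing might mean image acquisition time, which could vary within a patient. However, the SAP defines no such variable, and the lead-in to 13.1 speaks of administration. If acquisition time was meant, it needs a definition, so the sentence must change either way.

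Finally, SAP 2.1 places table specifications and any example code in a separate document that was not available here. The coding may be settled there, but the SAP sentence would still need correcting.

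**Conclusion.** The concern holds. As written, the RMANOVA assigns timing to the wrong stratum. That conclusion rests only on the cohort structure and the SAP's own timing measures, not on any assumed value.

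The size of the consequence is conditional. If timing is tested against within-patient error, the type I error is 13%-69% over 3-10 images per patient and ICC 0.2-0.7 (42% at 5 images and ICC 0.5). For any positive within-patient correlation the direction is anti-conservative. If timing is entered between patients, the problem largely disappears.

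Severity is minor: this is a secondary objective in an unpowered study, and a correct patient-level test is already planned.

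**What to change.** 1. Delete timing from the list of repeated factors in section 13.1.
2. State that the patient-level B1 v B2 comparison (Tables 14.2.4.1 and 14.2.4.2) is the governing analysis of timing.
3. If the image-level model is kept, fit it separately for Cohorts A and B, with patient as a random effect, images nested in patient, and a patient-by-method random effect.
   - **Cohort B:** timing cohort as a between-patient factor tested against between-patient variation (12 − 2 = 10 df), plus method, timing-by-method and device. The SAP does not say that every Cohort B patient is imaged with both cameras, so device should not be assumed to be within-patient.
   - **Cohort A:** method, without device, because for SBR "cohort A will only use images produced by Zeiss camera". If the dose cohorts are fitted together, add dose as a between-patient factor and report it descriptively.

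The patient-by-method term in step 3 matters. With the same m and ICC settings applied to FL−WLR differences (balanced data), the Cohort B timing-by-method test has type I error 0.049, 0.051 and 0.051 with the term, and 0.099, 0.276 and 0.498 without it.

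Steps 1 and 2 are sufficient to remove the error; step 3 is needed only if the model stays. The cost is SAP wording and no new data. Keeping the model means a little more modelling work and, if dose cohorts are pooled, a common variance across doses that cohorts of 3 cannot check.

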The aim is to determine the lowest possible dose that achieves adequate imaging performance (nerve identification) with an acceptable toxicity profile. The Safety Review Committee (SRC) will determine the Optimal Dose based on 1) the safety data and 2) adequacy of fluorescence observed in each of the dose groups. Following determination of the Optimal Dose, Dose Timing Cohorts will

QMS Document Name: Statistical Analysis Plan	Page 8 of 29
QMS No (include version ref): STF-015-GL.02	Document date: 09JUL2019
CONFIDENTIAL	

commence at this Optimal Dose. The Dose Timing Cohorts will compare fluorescence characteristics at different ALM-488 administration times before surgery (3-5 hours, 1-3 hours).

Please refer to Section 5 of the protocol for full details on the study design.

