### **6.2 Secondary Objectives**

- To characterize the PK of ALM-488 in subjects undergoing head and neck surgery.
- To determine the dose of ALM-488 needed to generate an adequate fluorescence signal in nerves.
- To evaluate the effect of timing of administration of ALM-488 relative to surgery (e.g., up to 5 hours before surgery) on adequacy of fluorescence nerve labeling.

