#### **12 Determination of Optimal Dose**

The optimal dose will be the lowest possible dose and toxicity profile that achieves adequate imaging performance: (1) DLT rate is 0 subjects for a 3-patient cohort (2) adequate fluorescence signal of nerves compared to background non-nerve tissue. A dot plot will be presented to display Cohorts A1 through A6. Cohorts A1 through A6 will be displayed on the x-axis, with a cluster of 3 to 6 dots for each cohort. The dose will be displayed on the y-axis. Dots will be open circles for subjects who do not experience a DLT. Solid red dots will be used for subjects who experience a DLT. A listing of the DLTs will also be provided.

Image intensity ratios will also be plotted with time from injection to skin incision on the x-axis, image intensity ratio on the y-axis, and a separate color for each dose level.

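### The SBR analyses said to inform the choice of dose contain no dose term, so the secondary dose objective gets no dose-effect estimate with a confidence interval

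*SAP*

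**What the plan says.** SAP 6.2 lists as a secondary objective: "To determine the dose of ALM-488 needed to generate an adequate fluorescence signal in nerves". SAP 13.1 states that timing, dose, SBR and the surgeon rating "will be assessed throughout enrollment into Cohorts A1-A6 to determine the final dose for use in Cohorts B1 and B2". It then plans these tests and models of SBR:

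- **Within each cohort:** SBR is averaged to one value per patient, "then a paired t-test or Wilcoxon signed rank test will be used, as appropriate, to compare SBR between FL and WLR".
- **Repeated measures ANOVA:** specified "with timing, image, method (FL /WLR), and device (Zeiss/OnLume) as the repeated factors in the model". Dose or cohort is not named.
- **Between cohorts:** "To further assess timing, Cohorts B1 and B2 will be compared", separately for FL and WLR.

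SAP 13.1 and 13.2 add an ROC cut-off and a correlation of SBR with the surgeon rating, each produced by cohort and for Cohort A as a whole. SAP 13 limits Cohort A SBR analyses to Zeiss images.

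The decision itself belongs to the SRC, which "will determine the Optimal Dose based on 1) the safety data and 2) adequacy of fluorescence observed in each of the dose groups". SAP 12 gives the imaging criterion as "adequate fluorescence signal of nerves compared to background non-nerve tissue", beside a DLT count of zero. SAP 4.1 makes one step depend on whether imaging at 75 mg "becomes less adequate compared to 100mg as determined by the SRC".

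Doses are also displayed side by side. SAP 7.2 summarises SBR and surgeon rating for each of A1-A6, SAP 8.1 gives each cohort a column labelled with its dose, and Figures 14.3.2 and 14.3.3 plot SBR by dose.

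**The concern.** Section 13.1 is headed with both timing and dose. Timing gets a named two-group comparison and two tables (14.2.4.1 and 14.2.4.2). Dose, the factor that varies by design across Cohort A, gets no test, model term or interval. FL against WLR within one cohort asks whether fluorescence beats white light at that dose, which is a different question from how the FL signal changes with dose.

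Two things are at stake. First, the final report would answer a stated secondary objective with per-cohort summaries of 3-6 patients and no measure of uncertainty for the difference between doses. Second, if the ANOVA is run on Cohort A as a whole, dose differences go into between-patient variation and the FL effect is an average over unlike doses. All 12 Cohort B subjects receive the dose chosen from these data.

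**Working it through.** **1. The plan's own figures.** Dose cohorts: 3 × 3 = 9 to 6 × 6 = 36. Timing cohorts: 2 × 6 = 12. Total: 9 + 12 = 21 to 36 + 12 = 48. All agree with SAP 4.1. No power, effect size or SD is stated for SBR, so there is no power figure to reproduce.

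**2. Does any inferential SBR analysis contrast doses?**

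| Analysis (SAP 13.1, 13.2) | What it compares | Dose contrasted? |
|---|---|---|
| Paired t / signed-rank | FL v WLR within a cohort | No, dose is constant |
| Repeated measures ANOVA | Timing, image, method, device | No, dose not named |
| Unpaired t / rank-sum | B1 v B2 | No, both at the Optimal Dose |
| ROC cut-off, correlation | SBR v surgeon rating, by cohort and pooled | No |

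In Cohort A the device factor has one level (Zeiss), so it cannot be estimated there.

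**3. What the within-cohort tests can show.** The smallest two-sided signed-rank p is 2/2ⁿ: 0.25 at n = 3, 0.125 at n = 4, 0.0625 at n = 5 and 0.031 at n = 6. Under the Wilcoxon fallback a cohort of 3 to 5 cannot reach 0.05. The default is the paired t-test, which has no such floor.

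**4. What a dose model would add.** Assumptions, since the documents give no SD: one mean log2 FL SBR per patient, between-patient SD 0.3-0.5, 3 patients per dose. The doses 75, 100 and 200 mg are those named in SAP 4.1.

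- *Direct contrast of two cohorts.* Half-width = t(0.975, 4) × SD × √(2/3) = 2.776 × 0.8165 × SD = 2.267 × SD, which gives 0.68 (SD 0.3) to 1.13 (SD 0.5).
- *Slope over three doses.* log2 doses are 6.229, 6.644 and 7.644, with mean 6.839. Sxx = 3 × (0.610² + 0.195² + 0.805²) = 3.17. Half-width per doubling = t(0.975, 7) × SD/√Sxx = 2.365 × SD/1.782, which gives 0.40 to 0.66. Per-doubling figures are not comparable with a contrast of two doses, so scale them: 75 to 200 mg is log2(200/75) = 1.415 doublings, giving 0.56 to 0.94.
- *Dose as a factor, no assumed shape.* Three cohorts share one error term with 6 degrees of freedom: 2.447 × 0.8165 × SD = 1.998 × SD, which gives 0.60 to 1.00.

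So for 75 v 200 mg at SD 0.3 the half-width goes from 0.68 (direct) to 0.60 (factor) to 0.56 (log-linear). More of the gain comes from the shared error term than from the assumed shape.

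**5. The 75 v 100 mg step.** If only those two cohorts exist, the slope is the two-cohort contrast rescaled. log2(100/75) = 0.415, and 0.68/0.415 = 1.64 and 1.13/0.415 = 2.73 per doubling. Over the actual 0.415 doublings this is again 0.68 to 1.13. A model adds nothing at that step.

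**6. Detectable differences, in between-patient SD units (two-sided 0.05, 80% power).** A pairwise test needs 3.07 SD at 3 v 3 and 1.80 SD at 6 v 6. A linear trend needs a lowest-to-highest range of 2.75 SD (3 cohorts of 3), 1.73 (3 of 6), 2.11 (6 of 3) or 1.41 (6 of 6). The trend figures assume equally spaced means.

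**The case against.** The strongest reply is that this is a small phase 1/2 study with committee-led dose selection and no power claim. Descriptive comparison of doses is usual in that setting, and with 3 per cohort no pairwise test would detect less than about 3 SD with 80% power. That stands, and it is why an exploratory estimate is the right request and a formal test is not.

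Three stronger readings are tempting, but the documents do not support them.

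- *That no planned analysis compares doses, or that a scatter plot is the only display by dose.* SAP 7.2 and 8.1 put SBR and surgeon rating for A1-A6 in columns by dose. What is missing is an inferential or model-based comparison.
- *That the SAP cannot show the lowest adequate dose.* Adequacy is judged by the SRC at each dose. A steep slope is compatible with every dose, or none, being adequate, so a dose model would not settle it.
- *That WLR SBR could serve as a negative control because it should not depend on dose.* Nothing in the documents says so.

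Two limits remain. The ANOVA sentence lists repeated factors, and dose is between-patient, so its absence from that list is not conclusive by itself. But the same list includes timing, which is between-patient in Cohort B, and no between-patient factor is named anywhere. Table specifications sit in a separate document (SAP 2.1), and the design detail is in protocol Section 5, which is not in the protocol text available here. Either might add a dose comparison or a definition of adequacy.

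**Conclusion.** The point holds as a gap in the specified analyses. Section 13.1 offers its SBR analyses as a basis for the final dose, but no test or model in it contains dose, and its ANOVA names a device factor that cannot vary in Cohort A. The secondary dose objective is left with descriptive summaries and no dose-effect estimate with an interval.

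The size is modest. With SD 0.3-0.5 log2 units and 3 patients per dose (both assumed for illustration), the half-width for 75 v 200 mg falls from 0.68-1.13 to 0.56-0.94, a reduction of about 17% (0.56/0.68 ≈ 0.83), and part of that depends on a log-linear shape. There is no gain when only 75 and 100 mg have been studied. The benefit grows with more cohorts or 6 per cohort. The change is worth making because it answers a stated objective at little cost. The lack of a dose term does not invalidate the SRC's process.

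**What to change.** In SAP 13.1:

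1. For the Cohort A repeated measures ANOVA, drop device and add dose (cohort) as a between-patient factor, with a dose-by-method (FL/WLR) term.
2. Add one model, labelled exploratory, of per-patient mean FL SBR (Zeiss images) on log dose across all Cohort A subjects in the FAS. Report the slope and the mean at each dose, all with 95% CIs.
3. State that these results support the SRC's adequacy judgement and the final report, and do not replace that judgement.
4. Add the matching table to SAP 20.1.

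If the sponsor prefers not to model dose, the least change is to say in 13.1 that doses are compared descriptively only.

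The cost is SAP wording and one extra table, with no new data or patients. The downside is the log-linear shape, which few cohorts can check. Showing the per-dose means beside the slope lets the reader judge it.
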